RIDGEBACKBIO

Long title: The Safety of EIDD-2801 and Its Effect on Viral Shedding of SARS-CoV-2

Short title: The Safety of EIDD-2801 and Its Effect on Viral Shedding of SARS-CoV-2

(The END-COVID Study)

Ridgeback Biotherapeutics Protocol #: EIDD-2801-2004

Clinical Phase: 2

ClinicalTrials.gov Identifier: NCT04405739

IND Sponsor/Principal Investigator:

Sponsor: Ridgeback Biotherapeutics LP

Principal Investigator: [name]

IND Number: 147734

Study Drug: EIDD-2801 and Placebo Capsules

Version/Date of Issue: Amendment 6, Version 7.0, 18 May 2021

Confidential Information: The information contained in this document is the property of Ridgeback Biotherapeutics LP and may not be reproduced, published, or disclosed to others without written authorization from Ridgeback Biotherapeutics LP.

PROTOCOL SUMMARY

Sample Size: 84 with allowance to increase up to 15% over as needed for dropouts or logistics considerations.

Study Population:

Adults aged 18 years or older who are hospitalized with a new diagnosis of coronavirus disease-2019 (COVID-19) with a duration of symptoms ≤7 days. Patients requiring admission to an intensive care unit or mechanical ventilation are not eligible.

Study Duration:

Length of study: Approximately 10 months from First Participant First Visit to Last Participant Last Visit

Length of participation of study participants: Up to 30 days, including a 0 to 2-day screening window, 5 days of dosing with study drug, and 23 days of post-dosing follow-up.

Locations:

Johns Hopkins Health System, The University of California, Los Angeles, and up to 5 additional sites in the United States

Study Design:

Phase 2a randomized, placebo-controlled, double-blinded clinical trial of EIDD-2801 (also known as MK-4482) in adult men and women who have tested positive for severe acute respiratory syndrome-coronavirus-2 (SARS-CoV-2) infection by polymerase chain reaction (PCR) test within 6 days (144 hours) prior to randomization and are hospitalized with a diagnosis of COVID-19. Rapid enrollment and treatment will be initiated such that the first dose of EIDD-2801 or placebo will be administered as soon as possible and within 7 days of onset of symptoms.

Randomization

Participants will be enrolled in up to 4 sequential study parts. During Part 1, participants will be randomized in a 1:1:1 ratio to: 200 mg EIDD-2801:400 mg EIDD-2801:placebo. In Part 2 of the study, 21 participants will be randomized in a 2:1 ratio to receive EIDD-2801 400 mg or placebo and in Part 3 of the study, 21 participants will be randomized in a 2:1 ratio to receive EIDD-2801 800 mg or placebo. An optional Part 4 may be added during which 21 participants will be randomized in a 2:1 ratio to EIDD-2801:placebo and the dose of EIDD-2801 may be the same or lower than doses studied in previous Part(s), but not to exceed 800 mg BID.

The study parts will be conducted as follows: Enrollment into Part 1 of the study may be terminated upon approval and implementation of Protocol Amendment 3, and enrollment into Part 2 will be initiated immediately thereafter. Enrollment into Part 3 will be initiated once Part 2 has been fully enrolled. If initiated, Part 4 may begin enrolling participants as soon as Part 3 has been fully enrolled. Study Parts 2 and 3 may be terminated prematurely based on emerging data from this and other ongoing studies of EIDD-2801.

Version: 7.0

Study Drug:

• EIDD-2801 and matching placebo

Primary Efficacy Objective:

To test whether orally administered EIDD-2801 results in a greater proportion of clearance from nasopharyngeal (NP) swabs compared to placebo in hospitalized adults by achieving undetectable (below the limit of detection [LOD] of the assay) viral RNA by Day 5 after initiation of study drug.

Primary Efficacy Endpoint:

Achievement of undetectable (below the LOD of the assay) SARS-CoV-2 RNA by Day 5 in NP swabs by quantitative reverse transcription polymerase chain reaction (qPCR).

Primary Safety Objective:

To evaluate the safety of treatment with EIDD-2801 in participants diagnosed with COVID-19

Primary Safety Endpoints:

- 1. Adverse events (AEs)
- 2. Serious adverse events (SAEs)
- 3. Physical examination including vital signs
- 4. Safety laboratory assessments
 - complete blood counts (CBC) with differentials
 - decrease in hemoglobin (Hgb) by >1 g/dL, or to <9 g/dL
 - decrease in platelet count by $50,000/\mu$ L, or to $<75,000/\mu$ L
 - comprehensive metabolic panels (CMP) including liver function tests
 - increase in aspartate aminotransferase (AST), alanine aminotransferase (ALT), amylase, or lipase to $\ge 3x$ the upper limit of normal (ULN)
 - urinalysis
- 5. Electrocardiograms (ECGs)

Secondary Virologic Objectives:

To evaluate the efficacy of EIDD-2801 on clearance of SARS-CoV-2 RNA.

Secondary Virologic Endpoints:

- 1. Time to clearance of viral RNA in NP swabs
 - by qPCR
- 2. The decline in viral RNA by Day 3, Day 5, Day 8, Day 11, Day 15, Day 19, and Day 28 after initiation of study drug in NP swabs
 - by qPCR

Version: 7.0

3. Rate of decline in viral RNA (change in log₁₀ copies/mL per day) in NP swabs – by qPCR

Secondary Clinical Objective

To evaluate the effect of EIDD-2801 on improvement of clinical symptoms and signs of COVID-19.

Secondary Clinical Endpoints:

- 1. Peak stage on the World Health Organization (WHO) Ordinal Scale for Clinical Improvement (Appendix 1) OR clinical requirement for addition of other antivirals including but not limited to:
 - Pegylated interferon alpha
 - Inhaled interferon beta1
 - Ribavirin (any formulation)
 - Any interleukin (IL)-6 inhibitor
- 2. Number of days of supplemental oxygen
- 3. Number of days of mechanical ventilation
- 4. Number of days in the Intensive Care Unit (ICU)
- 5. Death

Exploratory Virologic Objective

To evaluate the efficacy of EIDD-2801 to clear SARS-CoV-2 RNA and infectious virus.

Exploratory Virologic Endpoints:

- 1. Achievement of undetectable(below the LOD of the assay) viral titers by Day 5 in NP swabs
 - by infectivity assay
- 2. Time to clearance of infectious virus in NP swabs
 - by infectivity assay
- 3. Clearance of infectious virus by Day 3 and Day 5 in NP swabs
 - by infectivity assay
- 4. The number of acquired single-nucleotide polymorphisms in SARS-CoV-2 genomes by Day 5 or Day 11 in NP swabs
 - by viral sequencing

Exploratory Clinical Objective

To ascertain the role of EIDD-2801 in improvement of clinical symptoms and signs of COVID-19.

Exploratory Clinical Endpoints:

- 1. Days of hospitalization
- 2. Time until on room air without requirement for supplemental oxygen
- 3. Time to resolution of COVID-19 symptoms defined as:
 - Fevers OR

Version: 7.0

- At least one of the following symptoms: cough, shortness of breath, respiratory rate ≥20, radiographic evidence of pneumonia OR
- other clinical symptoms or signs of pneumonia that are not otherwise explained by comorbidities or co-diagnoses
- 4. Number of days until a 2-point decrease in stage according to the WHO Ordinal Scale for Clinical Improvement (Appendix 1).
- 5. Radiologic improvement by grading chest diagnostics (when radiography is available)
- 6. Change in interleukin (IL)-6 levels by Day 5

Pharmacokinetic Objectives

(To be conducted in a subset of participants at clinical sites that can participate, including but not limited to on Days 3 to 4 of dosing):

Secondary:

To evaluate EIDD-1931 pharmacokinetics in plasma.

Exploratory:

To characterize the pharmacokinetics of EIDD-2061 (NHC-TP) in peripheral blood mononuclear cells (PBMC) in a subset of participants.

Pharmacokinetic Endpoints:

Secondary (plasma analysis):

- 1. Maximum EIDD-1931 concentration (C_{max})
- 2. 1.5-hour EIDD-1931 concentration (C_{1.5})
- 3. 3-hour EIDD-1931 concentration (C₃)
- 4. Area under the concentration: time curve of EIDD-1931 (AUC)
- 5. Elimination half-life (t_{1/2}) of EIDD-1931

Exploratory (PBMC analysis):

- 1. Maximum EIDD-2061 concentration (C_{max})
- 2. EIDD-2061 time of maximal concentration (t_{max})
- 3. Elimination half-life of EIDD-2061 ($t_{1/2}$)
- 4. Area under the concentration: time curve of EIDD-2061 (AUC₀₋₁₂)
- 5. Parent: metabolite (EIDD-1931:EIDD-2061) concentration ratio at each time point, in which both plasma and PBMC are processed for PK analysis

Version: 7.0

TABLE OF CONTENTS

SPONSOR APPROVAL	2
SIGNATURE PAGE	3
PROTOCOL SUMMARY	4
TABLE OF CONTENTS	8
LIST OF APPENDICES	11
LIST OF FIGURES	11
LIST OF ABBREVIATIONS	12
1. STUDY OBJECTIVES	14
1.1. Primary Efficacy Objective	14
1.2. Primary Safety Objective	14
1.3. Secondary Virologic Objective	14
1.4. Secondary Clinical Objectives	15
1.5. Exploratory Virologic Objective	15
1.6. Exploratory Clinical Objective	16
1.7. Pharmacokinetic Objectives	16
2. BACKGROUND AND SCIENTIFIC RATIONALE	18
2.1. Abstract	18
2.2. Background	19
2.3. Known Potential Risks	20
2.3.1. Clinical Findings	20
2.3.2. Nonclinical Findings	21
2.3.3.	25
2.4. Known Potential Benefits	26
2.4.1. Potential Benefits of Treatment	26
2.4.2. Potential Benefits of Clinical Monitoring and Virologic Testing	27
3. PATIENT POPULATION	28
3.1. Inclusion Criteria for Enrollment	28
3.2. Exclusion Criteria for Enrollment	29
4. INVESTIGATIONAL PLAN	32
4.1. Definitions	32
4.2. Randomization and Blinding	32
4.3. Intervention.	33
4.3.1. Screening	33

	4.3.	2. Administration of Study Drugs	33
	4.3.	3. Virologic Assessments	33
	4.3.	4. Clinical Assessments	34
	4.4.	Pregnancy Testing	34
	4.5.	Serology	35
	4.6.	Rationale for Medication Dosing	35
	4.7.	Concomitant Medications	35
	4.8.	Study Discontinuation	35
5.	PHA	ARMACEUTICAL INFORMATION	37
	5.1.	Agent Accountability	37

BiPAP: Bilevel positive airway pressure

BMI: Body mass index, or weight in kilograms divided by height in meters squared

C_{1.5}: One point five-hour concentration

C₃: Three-hour concentration

CDC: United States Centers for Disease Control and Prevention

CFR: Code of Federal Regulations

CHKV: Chikungunya virus

CLIA: Clinical Laboratory Improvement Amendment of 1988

C_{max}: Maximum concentration

COI: Conflict of Interest

CoV: Coronavirus

COVID-19: Coronavirus Disease

CRF: Case Report Form

CRS: Cytokine Release Syndrome DMC: Data Management Center

DRF: Dose range finding

ECG: Electrocardiogram

EEEV: Eastern equine encephalitis virus EUA: Emergency Use Authorization FDA: Food and Drug Administration

GCP: Good Clinical Practice HBV: Hepatitis B virus

HCV: Hepatitis C virus

HIV: Human immunodeficiency virus

IB: Investigator's Brochure I/E: Inclusion and exclusion

ICF: Informed Consent (Informed Consent Form)

ICU: Intensive Care Unit

IEC: Independent ethics committee IRB: Institutional review board

Version: 7.0 18 May 2021

IWRS: Interactive web response system

LOD: Limit of detection

MAD: Multiple ascending dose

MERS: Middle East Respiratory Syndrome

MERS-CoV: Middle East Respiratory Syndrome Coronavirus

MTD: Maximum tolerated dose

NOAEL: No observed adverse effect level

NP: Nasopharyngeal

PFA: Plaque forming assay

PO2: Partial pressure of oxygen

QD: Quaque die, or once daily

QOD: Quaque altera die, or once every other day

qPCR: Quantitative polymerase chain reaction

RSV: Respiratory syncytial virus

RT-PCR: Reverse transcriptase polymerase chain reaction

SAD: Single ascending dose SAE: Serious adverse event

SARS: Severe Acute Respiratory Syndrome

SARS-CoV: Severe Acute Respiratory Syndrome Coronavirus

SARS-CoV-2: Severe Acute Respiratory Syndrome Coronavirus 2

SOC: Standard of care

SRC: Safety review committee

t_{1/2}: half-life

VEEV: Venezuelan equine encephalitis virus

ZIKV: Zika virus

1. STUDY OBJECTIVES

1.1. Primary Efficacy Objective

Primary Efficacy Objective:

To test whether orally administered EIDD-2801 results in a greater proportion of clearance from nasopharyngeal (NP) swabs compared to placebo in hospitalized adults by achieving undetectable (below the limit of detection [LOD] of the assay) viral RNA by Day 5 after initiation of study drug.

Primary Efficacy Endpoint:

Achievement of undetectable (below the LOD of the assay) severe acute respiratory syndrome-coronavirus-2 (SARS-CoV-2) RNA by Day 5 in NP swabs by quantitative reverse transcription polymerase chain reaction (qPCR).

1.2. Primary Safety Objective

Primary Safety Objective:

To evaluate the safety of treatment with EIDD-2801 in participants diagnosed with COVID-19

Primary Safety Endpoints:

- 1. Adverse events (AEs)
- 2. Serious adverse events (SAE)
- 3. Physical examination including vital signs
- 4. Safety laboratory assessments:
 - complete blood counts (CBC) with differentials
 - decrease in hemoglobin (Hgb) by >1 g/dL, or to <9 g/dL
 - decrease in platelet count by $50,000/\mu$ L, or to $<75,000/\mu$ L
 - comprehensive metabolic panels (CMP) including liver function tests
 - increase in aspartate aminotransferase (AST), alanine aminotransferase (ALT), amylase, or lipase to ≥3x the upper limit of normal (ULN)
 - urinalysis
- 5. Electrocardiograms (ECGs)

1.3. Secondary Virologic Objective

To evaluate the efficacy of EIDD-2801 on clearance of SARS-CoV-2 RNA.

Version: 7.0

Secondary Virologic Endpoints:

- 1. Time to clearance of viral RNA in NP swabs
 - by qPCR
- 2. The decline in viral RNA by Day 3, Day 5, Day 8, Day 11, Day 15, Day 19, and Day 28 after initiation of study drug in NP swabs
 - - by qPCR
- 3. Rate of decline in viral RNA, (change in log₁₀ copies/mL per day) in NP swabs
 - - by qPCR

1.4. Secondary Clinical Objectives

To evaluate the effect of EIDD-2801 on improvement of clinical symptoms and signs of COVID-19.

Secondary Clinical Endpoints:

- 1. Peak stage on the World Health Organization (WHO) Ordinal Scale for Clinical Improvement (Appendix 1) OR clinical requirement for addition of other antivirals including but not limited to:
 - Pegylated interferon alpha
 - Inhaled interferon beta1
 - Ribavirin (any formulation)
 - Any interleukin (IL)-6 inhibitor
- 2. Number of days of supplemental oxygen
- 3. Number of days of mechanical ventilation
- 4. Number of days in the Intensive Care Unit (ICU)
- 5. Death

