4. INVESTIGATIONAL PLAN

4.1. Definitions

- I. Enrolled: From time consented to initiation of study drug until designated as off study either through discontinuation or completion of the study.
- II. Randomized: when a patient identification (ID) number is assigned through randomization.
- III. Screen Failures: signed informed consent, but then determined to be ineligible or withdraws before initiation of study drug.
- IV. Discontinued: randomized, but then withdrawn by investigator or withdraws consent.
- V. Completed: Participants are considered completed when they are followed through to Day 28 or died before that.

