4.7. Concomitant Medications

Nucleos(t)ide analog drugs that are used for the treatment or prevention of HIV or hepatitis B virus are prohibited during the study, as are vaccines against COVID-19.

Remdesivir will be permitted. Corticosteroids for the treatment of COVID-19 will be permitted.

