- c. For women of child-bearing potential only, high sensitivity serum pregnancy tests are required at Screening within 24 hours of the first dose of study drug and on Day 28. Additional serum or urine pregnancy tests may be performed, as determined necessary by the investigator or required by local regulation, to establish the absence of pregnancy at any time during the subject's participation in the study.
- d. Serology testing will be performed on plasma for immune response on Day 1 (pre-dose), Day 5, and Day 19, and specimens will be archived for further cytokine testing in the future.
- e. The sample should be collected pre-dose.
- f. EIDD-2801 and PBO are to be administered BID on Days 1-5. The first dose will be administered in the morning of Day 1, if possible. If the first dose is given later in the day, the second dose may be given at least 4 hours later on Day 1. If the first dose on Day 1 is given in the late evening, the second dose may be taken on the morning of Day 2, in which case the final dose will be taken on the morning of Day 6. In the event of missed doses, if the total number of missed doses is 4 or fewer, the number of days of study drug can be extended by no more than 1 day (through Day 6) for the equivalent of missed doses up to 2 doses. If the participant misses more than 4 consecutive doses, or more than 5 total doses, then the participant will be discontinued from any further study drug administration and followed for safety for the remainder of the study.
- g. One NP swab will be collected from each nostril at each time point for a total of 2 swabs per time point.
- h. BAL and/or sputum fluid *may* be collected when available for viral RNA testing. No study specific interventions will be initiated for collection of BAL fluid and/or sputum if participant has a productive cough. If, during clinical care, BAL is performed and excess fluid is available, the study team will collect this fluid for testing.
- i. Note that on Day 1, the WHO ordinal scale assessment should be performed before the first dose of EIDD-2801 is administered.
- j. Clinical assessments will be ascertained by chart extraction and will include number of days in the hospital, maximum O₂ requirements daily, ICU admission and number of days in the ICU, mechanical ventilation and number of days requiring mechanical ventilation, death, and symptom reporting.

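### Secondary clinical endpoints 2 to 4 count support days with no allowance for death, and endpoint 1 joins two measures without defining one variable

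*Protocol*

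**What the plan says.** The secondary clinical objective in Protocol section 1.4 is "To evaluate the effect of EIDD-2801 on improvement of clinical symptoms and signs of COVID-19". Five endpoints follow.

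- Endpoint 1 is "Peak stage on the World Health Organization (WHO) Ordinal Scale for Clinical Improvement (Appendix 1) OR clinical requirement for addition of other antivirals". The antiviral part is an open list, worded as a "clinical requirement for addition of other antivirals including but not limited to" the examples given, which are two interferons, ribavirin and the IL-6 inhibitors.
- Endpoints 2 to 4 are counts of days on supplemental oxygen, on ventilation ("Number of days of mechanical ventilation") and in ICU. No follow-up length and no treatment of death is attached to them.
- Endpoint 5 is death.

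Other sections bear on these definitions:

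- Section 2.1 describes the same secondary outcomes but gives peak WHO stage and need for further antivirals as separate items.
- Section 4.1 says: "Participants are considered completed when they are followed through to Day 28 or died before that".
- Section 4.7 says: "Remdesivir will be permitted. Corticosteroids for the treatment of COVID-19 will be permitted".
- Footnote i of the inpatient schedule in section 7.1 says: "Note that on Day 1, the WHO ordinal scale assessment should be performed before the first dose of EIDD-2801 is administered".
- Appendix 1 gives death a score of 8, the worst on the scale.
- Section 6.2.7 has clinical endpoints summarised descriptively, with details left to the SAP. Section 8.1 says the study has no power for clinical outcomes.

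**The concern.** A count of days on support falls for two opposite reasons: the participant recovered, or the participant died. Read alone, endpoints 2 to 4 cannot tell these apart. An arm with more or earlier deaths can therefore show fewer days on oxygen, on a ventilator or in ICU. With about 14 participants in a dose group, a single death can move a mean visibly. Section 4.6 says that exploring several doses is meant to guide which are taken forward, so a summary that points the wrong way matters even without a test.

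Endpoint 1 has a different problem. An ordinal score and a yes/no event joined by OR do not give each participant one value, so two analysts could build different variables from the same text. The open list adds a second uncertainty, because an antiviral that the protocol permits as background care may or may not trigger the endpoint.

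**Working it through.** The protocol states no rate, effect size or power for the secondary clinical endpoints, so there is no figure of its own to reproduce. Its only power figure, in section 6.1, concerns the primary virologic endpoint and does not bear on this point. From the documents I take 14 participants per dose group (section 6.1) and a Day 28 horizon (section 4.1). Every other number below is an assumption.

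**Ventilation days, one participant.** If a participant who would have survived after S ventilated days instead dies after D, the arm mean changes by (D − S)/n.

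- With D = 3, S = 20, n = 14: (3 − 20)/14 = −1.21 days.
- With n = 21: −17/21 = −0.81. With n = 28: −17/28 = −0.61. Pooling dilutes the shift but does not change its sign.
- On a scale of days alive and ventilator-free to Day 28, with death scored zero, the survivor has 28 − 20 = 8 and the death has 0. The arm mean falls by 8/14 = 0.57 free days, which is the right direction.
- A participant who dies without ever being ventilated scores 0 ventilated days, the best possible value and the same as a survivor who never needed a ventilator.

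**Oxygen days, whole arm.** Assume survivors average 8 days on oxygen, deaths occur after 4 days on oxygen, and mortality is m. The crude mean is 8(1 − m) + 4m. The mean of oxygen-free days alive to Day 28 is (28 − 8)(1 − m) + 0·m.

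| m | crude oxygen days | oxygen-free days alive |
|---|---|---|
| 5% | 7.8 | 19.0 |
| 10% | 7.6 | 18.0 |
| 15% | 7.4 | 17.0 |
| 20% | 7.2 | 16.0 |

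As mortality rises from 5% to 20%, the crude count improves by 0.6 days while the free-day score worsens by 3.0.

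**Endpoint 1, sections side by side.** Section 1.4 joins the two parts by OR; section 2.1 lists them apart. Take participant A with peak stage 4 and ribavirin added, and participant B with peak stage 5 and nothing added. Section 1.4 gives no rank for added treatment on the scale, so A and B cannot be ordered. It also gives no cut-off on the scale, so the pair cannot be reduced to a yes/no event either.

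**Remdesivir and the open list.** Section 2.2 describes remdesivir as a nucleoside analogue that inhibits coronaviruses, so the protocol treats it as an antiviral. Section 4.7 allows it. Section 1.4 neither names nor excludes it. The listed examples do not settle the class, because IL-6 inhibitors appear among them under the antiviral label.

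Suppose every start after entry did count, independently of other need, in a share r of each arm. Suppose also that the true need was 10% v 25%. The rates for the antiviral part alone become 1 − 0.90(1 − r) and 1 − 0.75(1 − r), a difference of 0.15(1 − r):

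- r = 20%: 12 points.
- r = 40%: 46% v 55%, or 9 points.
- r = 60%: 6 points.

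This shows what rests on the ambiguity. It does not show that remdesivir is counted.

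**The case against.** The strongest reply is that much of this is SAP territory, and that the clinical analyses are descriptive and unpowered. Death is not hidden: it is endpoint 5, and it takes the worst score on the WHO scale used in endpoint 1. The definition of a completed participant in section 4.1 is a status definition, not a scoring rule. Section 3.2 excludes patients not expected to survive 24 hours, which limits very early deaths. If the day counts were summarised by medians, one death might not move them.

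Most of this stands as mitigation. It does not remove the point. The raw count is the endpoint that the protocol itself fixes, and reporting death elsewhere leaves endpoints 2 to 4 as they are. A median leaves the ordering of individual participants wrong. The OR and its disagreement with section 2.1 are also in the protocol's own text.

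Three stronger readings are tempting and are not supported.

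- A reader might infer that endpoint 1 counts permitted remdesivir. The text requires a clinical need for an addition, which fits escalation of care at least as well as routine background treatment, and remdesivir already running at entry is hardly an addition. The text is open on the matter; it does not say yes.
- A reader might infer that the pre-dose Day 1 stage enters the peak. Footnote i only fixes when that assessment is made, as for any baseline. The protocol is silent on the window, and an SAP ordinarily sets it.
- A reader might infer that the improvement objective cannot be answered. Support days carry information on clinical course, peak stage can register prevention of worsening, and section 1.6 has direct improvement measures as exploratory endpoints, including time to room air and days to a 2-point fall in WHO stage.

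**Conclusion.** The point holds as a moderate weakness in endpoint definition. Endpoints 2 to 4 can make a fatal course look better than a long recovery. The size is about 1.2 days on an arm mean for one such death among 14, under an assumed 3 v 20 ventilated days, and less in larger pooled groups. These figures are illustrative; no documented rate supports a particular between-arm bias in this trial.

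Endpoint 1 is not one computable variable as written, differs from section 2.1, and leaves the status of a remdesivir start unclear. These conclusions rest on the wording alone and need no assumed rates.

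**What to change.** - **Endpoints 2 to 4.** Replace or accompany each count with days alive and free of that support (oxygen, ventilation, ICU) through Day 28, scoring death by Day 28 as zero.
- **Endpoint 1.** Split it, in line with section 2.1, into (i) worst WHO stage after the first dose, compared with account of the Day 1 pre-dose stage, and (ii) added agents started after the first dose, stating that background therapies permitted in section 4.7 do not count.
- **Consistency.** Use the same wording in the Protocol Summary, sections 1.4 and 2.1, and the SAP.

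The cost is wording. Footnote j of the inpatient schedule in section 7.1 already has daily oxygen need, ICU days, ventilation days and death extracted from charts, and section 4.3.4 has concomitant medications, antivirals included, recorded. A convention for oxygen used at home after discharge is needed under either form. The downside is that free-day scores are slightly less direct to read than raw counts, which is a reason to show both.
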